TITLE: The effect of pretreatment with intravenous lidocaine for intravenous contrast: A double-blinded, randomized-control trial

NCT#:

Document Date: August 18, 2021

INTRODUCTION

The management of pain is a key aspect of pediatric emergency medicine. Oftentimes, the pain is a result from medical procedures or interventions required in their treatment. Computerized tomography (CT) scans with intravenous (IV) contrast-media is a common procedure required to diagnose many common pediatric pathologies such as retropharyngeal abscess and appendicitis that can lead to discomfort and pain. Because of this discomfort and pain, pediatric patients are often unable to remain still during the infusion of IV contrast and require procedural sedation, which increases the patient's risk for adverse effects. The current standard of care involves no medication to prevent or mitigate IV contrast associated discomfort. This double-blinded, randomized controlled study attempts to determine if an infusion of IV lidocaine prior to IV contrast will reduce pain when compared to placebo.

BACKGROUND AND SIGNIFICANCE

The management of pain is a key aspect of pediatric emergency medicine that is not only complex but also difficult to assess.¹ Many times, the pain comes from the medical procedures or interventions required in their treatment.² Moreover, studies have shown that due to the neuroplasticity of neonates and infants, poorly controlled pain can lead to hypersensitivity to pain later in life.^{3,4} It is therefore vital to identify methods and strategies to reduce pain in pediatric emergency care.

Intravenous contrast-media is a commonly used for CT scans for improved image clarity in pediatric emergency medicine. At times, IV contrast-media is required in order to clearly delineate such processes as retropharyngeal abscess or appendicitis. IV contrast-media has been associated with multiple immediate negative effects including nausea, vomiting, warmth at the site of administration, and pruritus during infusion as well as delayed responses, such as anaphylaxis and nephrotoxicity.⁵⁻⁷ For the immediate reactions, these symptoms can be explained to many adults and adolescents; however, in the younger pediatric population especially under the age of 6 years old, it is difficult to explain and these symptoms, which can be perceived as frightening, uncomfortable, or painful. Children who feel discomfort during the administration of IV contrast media may not remain still during the CT scan, which affects the overall study quality and reliability. Therefore, many young patients often undergo procedural sedation in anticipation of movement artifact degrading the diagnostic accuracy. Procedural sedation, while a common procedure in the pediatric emergency department, does have significant complications, and it increases the risk of adverse events for the patient.^{8,9} The risk of airway compromise associated with procedural sedation is particularly concerning in children requiring IV contrast for imaging of an upper airway pathology such as retropharyngeal abscess, as the disease itself narrows the airway. This presents the physician with a dilemma of assessing the extent of disease without the additional risk of airway compromise by using procedural sedation.

Previous research has looked at premedication with steroids prior to IV-contrast media administration to avert an allergic response.¹⁰ However, there has been no investigation of premedication to abate the immediate adverse effects of discomfort associated with IV contrast injection. Propofol is a commonly administered medication in the emergency department known to cause pain at the injection site, the administration of which often includes pretreatment with intravenous lidocaine in order to mitigate the infusion's burning sensation.^{11,12} The safety of IV lidocaine in pediatric patients has been documented in studies of its use for post-operative pain, using doses from 1.0 to 1.5 mg/kg with no known adverse side effects.^{13,14} CT scans with IV contrast are performed on a near daily basis in the Maimonides pediatric

emergency department, usually for the assessment of acute appendicitis. The standard of care in children and adults receiving IV contrast does not include pre-medication to prevent IV contrast-associated discomfort. This double blinded prospective study aims to determine whether pre-treatment with lidocaine can mitigate the immediate discomfort of IV contrast in verbal children and adolescents who can comply with a pre and post IV contrast pain assessment. Moreover, this study also has the ability to be extrapolated to adult patients as the adverse effects of IV-contrast are similar. The aim of this investigation is to identify a pain-free experience for pediatric patients, obviating the need for sedation in younger patients, and improving the overall quality of care.

STUDY OBJECTIVES

- To improve patient's comfort during CT scans
- To promote and encourage "pain-free" emergency departments
- To develop a protocol to improve pediatric patients' compliance for CT scans without requiring procedural sedation

HYPOTHESIS

Pretreatment with intravenous lidocaine when compared to the placebo (normal saline) will reduce pain and discomfort after infusion of intravenous contrast media.

STUDY DESIGN

Subjects: Patients aged from 7 to 17 years-old who present to the Maimonides Medical Center's Emergency Department that require a CT scan with IV contrast. Research team members will be notified when the patient requires CT scan with IV contrast and meets the eligibility criteria. Potential subjects will be recruited in the Emergency Department

Eligibility Criteria: Inclusion criteria: Patients with age of 7 to 17 years-old who require a CT scan with IV contrast. Exclusion criteria: Patients with history of seizures, cardiovascular disease, presenting as a trauma, a history of anaphylaxis to lidocaine, or children/adolescents with underlying neurodevelopmental conditions which would interfere with their ability to respond to pre and post IV contrast pain assessments.

Design: This is a prospective, double-blinded randomized control study that will be comparing intravenous lidocaine to a placebo. Patients will be randomized with block randomization. The randomization list will be generated EM Research Manager and given to the EM pharmacist a priori of commencement of the study. The EM Research Manager and EM Pharmacist are not blinded to the study. Once a potential subject has been identified, a member of the research team will obtain consent from the parent or guardian of the subject. The research team member involved with consent and data collection, provider, and subject will all be blinded to which treatment arm they are assigned.

The research team members will monitor each patient and in conjunction with the pharmacy will deliver the assigned treatment to the subject's nurse to administer 10 min prior to the CT scan. If selected for the treatment group, the patient will receive a 1mg/kg IV dose of lidocaine with a max dose of 40mg.¹⁵ A patient selected to the control group will an equal volume of normal saline infused. A research team member will be present during the administration of assigned treatment until the completion of the CT scan. The

patient will be placed on a cardiopulmonary monitor for the duration of this period. Advanced airway equipment, IV midazolam, and IV intralipids will also be available at bedside during infusion and until completion of CT scan to treat any potential adverse effect associated with lidocaine.

Nominal variables to be collected include gender, chief complaint, pain score at triage, use of pain medication at triage and during the ED course, diagnosis, type of CT scan performed, pre and post-intervention pain score, post-intervention pruritus score, post-intervention burning pain score. The only continuous variable being collected includes age (in years-old).

There will be no interruption or deviation from the standard of clinical care provided to each subject. This study will be run completely in the Pediatric Emergency Department.

Data Collection Procedures: Once a subject has been enrolled, the research team member will review the chart and collect all pertinent information as shown in the data collection template. A questionnaire will be completed prior to administration of the medication as well as following the CT scan which will be administered by the research team member. We will use a combination of the Baker-Wong FACES pain scale and 1 to 10 numerical scale for pain as well as a 5-point Likert scale for discomfort. Once all data has been collected, it will be recorded in password protected document located on a secure server only accessible to members of the research team. All information about the patients will be de-identified. Study investigators will record pain scores, vital signs, and adverse effects at prior to intervention, immediately following intervention, and 15 min following the intervention

The preparing ED pharmacist, research manager, and statistician will be the only ones with knowledge of the study arm to which each participant would be randomized. Treating providers, participants, and the data collecting research team will be blind to the medication route received.

All data will be recorded on data collection sheets, including patients' gender, demographics, medical history, and vital signs, and entered into SPSS (version 27.0; IBM Corp) by the research manager. Development of the randomization list, confirmation of written consent acquisition for all participants, and statistical analyses will be conducted by the research manager and statistician who will work independently of any data collection.

Patients will be closely monitored for any change in vital signs and for adverse effects during the entire study period (up to 120 minutes) by study investigators.

Data Analysis: Data analyses will include frequency distributions, paired t-test to assess a difference in pain scores within each group, and independent-sample t-test to assess differences in pain scores between the 2 groups at the various intervals. Mixed-model linear regression will be used to compare changes in pain numeric rating scale across time points. This will compensate for participants lost to follow-up and allow all patients' data to be analyzed on an intention-to-treat principle. For categorical outcomes (e.g., complete resolution of pain), a χ^2 or Fisher's exact test will be used to compare outcomes at 30 minutes. Percentage differences and 95% confidence intervals between the treatment groups will be calculated for all time points with $P < 0.05$ to denote statistical significance.

REFERENCES

2. Health C on PA of C and F, Task Force on Pain in Infants C. The Assessment and Management of Acute Pain in Infants, Children, and Adolescents. *Pediatrics*. 2001;108(3):793-797. doi:10.1542/peds.108.3.793
3. Wilson-Smith EM. Procedural Pain Management in Neonates, Infants and Children. *Rev Pain*. 2011;5(3):4-12. doi:10.1177/204946371100500303

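### ED analgesic use is not split at study drug and enters no analysis, so pre-dose analgesia and post-dose rescue cannot be told apart in the listed data

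*Combined protocol and SAP*

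**What the plan says.** The list of nominal variables in Study Design (Design) includes "use of pain medication at triage and during the ED course". That gives two labels, triage and ED course. No drug, dose or clock time is named, and the ED-course label is not divided at study drug, at contrast or at any pain score.

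The same section states: "There will be no interruption or deviation from the standard of clinical care provided to each subject". No section restricts or standardises other analgesia. The exclusions ("Patients with history of seizures, cardiovascular disease, presenting as a trauma, a history of anaphylaxis to lidocaine", then neurodevelopmental conditions that would impede pain assessment) do not mention recent analgesic use.

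On timing, study drug goes to the nurse "to administer 10 min prior to the CT scan". Data Collection Procedures has pain scores recorded "prior to intervention, immediately following intervention, and 15 min following the intervention", and a questionnaire after the CT with no clock time. Data Analysis places the categorical comparison at 30 minutes.

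Data Analysis names paired t-tests, an "independent-sample t-test to assess differences in pain scores between the 2 groups at the various intervals", a mixed model under intention-to-treat, and chi-square or Fisher tests. Analgesic use appears in none of them, and nothing says how a score taken after other analgesia is handled.

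**The concern.** Background and Significance says these scans are usually done to assess appendicitis. Many children may therefore already be in pain from their illness, and the pain scales are not confined to pain from contrast. An ED analgesic can move the score whatever the arm.

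Analgesia before study drug cannot be affected by the assigned arm. It is balanced in expectation, adds variation, and is a legitimate covariate. Analgesia after study drug may depend on how well the assigned treatment worked, so it is an outcome. With both under one label, adjusting for the field would partly condition on a consequence of treatment, and ignoring it gives up precision. A small or null difference could then not be told apart from one that rescue had masked. An analgesic given for the presenting illness could also produce full resolution of pain at 30 minutes, and the listed data would not show it.

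**Working it through.** The documents give no sample size, SD, target difference or rescue rate, so there is no stated figure to reproduce.

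**Step 1: what the listed field can separate.**

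| When the analgesic is given | Label | Statistical role |
|---|---|---|
| Triage | triage | baseline |
| ED, before study drug | ED course | baseline |
| ED, between study drug and a pain score | ED course | possible consequence of the arm |
| ED, after the last score | ED course | cannot affect any score |

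Three periods with different roles share one label.

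**Step 2: time available for rescue to act.** Take the intervention to be study drug at minute 0, with contrast at about minute 10.

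- 15-minute score: 15 − 10 = 5 minutes for contrast pain to prompt rescue and for rescue to work.
- 30-minute comparison: 30 − 10 = 20 minutes.
- Post-CT questionnaire: no clock time, so no stated limit.

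Rescue before contrast cannot be a response to contrast pain. It would differ by arm only if lidocaine relieved the presenting pain. Any dilution therefore falls mainly on the 30-minute comparison and the questionnaire.

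**Step 3: illustrative size for a mean score.** All inputs here are assumptions.

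Observed difference = D − g × (r_saline − r_lidocaine), where D is the difference without rescue, g the points of relief from rescue, and r the proportion rescued before the score.

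Take D = 1.5, g = 2, SD 2.5 (held fixed), two-sided alpha 0.05, 1:1 allocation and 44 per arm, which gives about 80% power without rescue.

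| Excess rescue on saline | Observed difference | Lost | Power |
|---|---|---|---|
| 0 | 1.5 | 0% | 80% |
| 5% | 1.5 − 2 × 0.05 = 1.40 | 7% | 75% |
| 10% | 1.5 − 2 × 0.10 = 1.30 | 13% | 68% |
| 20% | 1.5 − 2 × 0.20 = 1.10 | 27% | 54% |
| 30% | 1.5 − 2 × 0.30 = 0.90 | 40% | 39% |

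Over g = 1 to 3 and 5% to 30% excess, the loss runs from 1 × 0.05 / 1.5 = 3% to 3 × 0.30 / 1.5 = 60%. The same grid gives 5% to 90% for D = 1.0 and 2.5% to 45% for D = 2.0. The direction carries over to the 30-minute categorical comparison, but these figures do not.

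**The case against.** The strongest reply has four parts.

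- **The record may be better than the list.** Triage use is labelled separately and is usable as a covariate now. The variable list is visibly incomplete: it calls age the only continuous variable, yet Data Collection Procedures also collects vital signs. The data collection template is not in the supplied text and may hold times, or times may be retrievable from the chart. This stands. A reader might infer that dosing times are never recorded and the field is beyond repair; the documents do not show that. They show only that the listed variable carries no split and that no analysis calls for one.
- **There is little time for rescue to act, and providers are blinded.** This stands for the 15-minute score. It has less force at 30 minutes and for the untimed questionnaire. Blinding removes rescue driven by knowledge of the arm, but not rescue driven by the child's pain.
- **Intention-to-treat already answers the question.** Under a treatment-policy reading, scores after rescue belong to the effect being estimated, and the diluted difference is valid. This stands, and is why the main analysis should not change. The reader still needs rescue by arm to interpret the result.
- **Timestamps do not permit a correction.** This is true for post-dose use, since adjusting for it could itself introduce bias. They do permit adjustment for pre-dose use and a report of post-dose use.

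A reader might also infer that steroid or antihistamine premedication distorts the pruritus score. Support is lacking: "Previous research has looked at premedication with steroids prior to IV-contrast media administration to avert an allergic response" describes earlier research, not practice at this site. Premedication before study drug is balanced in expectation, and Data Analysis names no pruritus analysis.

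**Conclusion.** The point holds as a gap in data definition and analysis, and it is cheap to close. The listed field does not separate analgesia before study drug from analgesia after it, and the analysis uses neither.

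It is tempting to conclude that rescue will shrink the pain difference. The documents do not support that: they give no rescue rates, and unrestricted analgesia is itself inferred from the promise of unchanged usual care. The conclusion is conditional. If post-dose analgesia is more frequent on saline and takes effect before the score, the observed difference is smaller than it would be without rescue. With equal rates and equal relief there is no bias, only added variance. The 3% to 60% range for a true difference of 1.5 rests wholly on assumed inputs, and the short window makes the upper end unlikely for the 15-minute score.

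**What to change.** 1. On the data collection sheet, record drug and clock time for each analgesic or sedative given in the ED, with the clock times of study drug, contrast and each pain score. If the template already holds these, say so in the protocol. Analgesic times should be available from the chart the team already reviews.
2. Split the field at study drug. Include pre-dose analgesic (yes/no) and the pre-dose pain score as covariates in the between-arm model of post-dose scores.
3. Report analgesic use after study drug and before each score by arm, as an outcome. Never use it as a covariate.
4. State that intention-to-treat, read as treatment policy, is the main analysis.
5. Add one sensitivity analysis with a single pre-specified rule for scores after rescue. The rule must not substitute a pre-contrast score: the last score before rescue may be the one taken immediately after study drug, which says nothing about contrast pain. Fix the rule before any outcome data are seen, because the statistician knows the arms.

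The cost is a few data fields, a few sentences in Data Analysis and one extra analysis. Clinical care does not change.

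### Complete resolution of pain is to be tested at 30 minutes, but the last timed pain score is at 15 minutes and neither time has a defined zero

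*Combined protocol and SAP*

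**What the plan says.** **Schedule.** Data Collection Procedures states: "Study investigators will record pain scores, vital signs, and adverse effects at prior to intervention, immediately following intervention, and 15 min following the intervention". The same section has a questionnaire before the study drug and another after the CT scan, using a faces scale, a numerical pain scale and a Likert scale for discomfort. It gives no clock time for the second questionnaire. It also describes monitoring for up to 120 minutes, for vital signs and adverse effects; pain is not listed there. Staff are to "collect all pertinent information as shown in the data collection template", but that template is not among the documents.

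**Variables and dosing.** The Design paragraph of Study Design lists a "pre and post-intervention pain score" without a clock time. The study drug is for the nurse "to administer 10 min prior to the CT scan".

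**Analysis.** Data Analysis plans a chi-squared or Fisher's "exact test will be used to compare outcomes at 30 minutes" for categorical outcomes, with complete resolution of pain given as an example. It also plans an "independent-sample t-test to assess differences in pain scores between the 2 groups at the various intervals", a mixed model across time points, and this: "Percentage differences and 95% confidence intervals between the treatment groups will be calculated for all time points".

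**Aim.** Background and Significance says the study asks "whether pre-treatment with lidocaine can mitigate the immediate discomfort of IV contrast".

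**The concern.** The categorical test is the only comparison in Data Analysis with a specific clock time, and for pain that time does not appear in the schedule. The word *intervention* is never tied to the study drug, the contrast or the scan, so a reader cannot tell which pain score is meant to feed the test.

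If the two times share a zero, someone will later have to drop the pain-resolution test, move it to another record or run it on unscheduled scores. The plan does not say which. The candidate records do not measure the same thing: depending on the zero, the score taken immediately after the intervention may come before or after contrast. The plan names no primary outcome or time point that would settle the choice. The research manager and statistician who run the analyses know the study arm, so the choice is better fixed in advance.

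**Working it through.** The plan states no figure to reproduce. The check sets the schedule against the analysis time and works out the timing.

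**Inputs from the documents**
- Timed pain scores: before, immediately after (0 min) and 15 min after the intervention (Data Collection Procedures).
- Categorical test: 30 min, zero not stated (Data Analysis).
- Study drug: 10 min before the CT scan (Design).

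**Assumptions**
- Contrast is given at CT start.
- D, the time from CT start to the end of the scan, is not given; a range is shown where it is used.

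**Step 1. Direct comparison.** Timed pain scores at 30 minutes: 0 of 3. The questionnaire after the scan is scheduled but untimed, so it is not a 30-minute assessment.

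**Step 2. Gap between the test and the last timed score.**

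Gap = (test zero + 30) - (record zero + 15) = 15 + (test zero - record zero).

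With a common zero the bracket is 0 and the gap is 15 minutes, whichever zero is chosen.

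**Step 3. What the scores measure under each common zero.**

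| Common zero | Score immediately after | Last timed score | Test time |
|---|---|---|---|
| Study drug, relative to planned CT start | 0 - 10 = -10 min | 15 - 10 = 5 min | 30 - 10 = 20 min |
| Contrast at CT start, relative to study drug | 10 + 0 = 10 min | 10 + 15 = 25 min | 10 + 30 = 40 min |

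Timed from the study drug, the score immediately after the intervention comes 10 minutes before the planned scan, so presumably before contrast, and only 1 of 3 scores can reflect contrast. Timed from contrast, 2 of 3 can.

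**Step 4. Can different zeros remove the gap?** Suppose the scores run from the end of the scan and the 30 minutes runs from the study drug. The last score is then at 10 + D + 15 = 25 + D minutes after the drug. For D assumed between 0 and 15 minutes this is 25 to 40 minutes, and it equals 30 only at D = 5. If instead the 30 minutes runs from CT start, the gap is 15 - D, which is zero only at D = 15. Agreement is possible, but it needs a pair of zeros and a scan duration that the plan does not state.

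**Step 5. The untimed questionnaire.** If the scan lasts an assumed 5 to 20 minutes, it ends 10 + 5 = 15 to 10 + 20 = 30 minutes after the drug. The questionnaire could therefore fall near 30 minutes after the drug, but by chance and at a different time for each child.

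**The case against.** The strongest case on the other side has four parts.

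- **Pain resolution is only an example.** Whether an adverse effect occurred is also categorical, and adverse effects are followed for up to 120 minutes, which can cover 30 minutes. A reader might infer that the whole 30-minute categorical comparison has no data. The documents do not support that; the gap concerns pain-based outcomes only. This part stands.
- **The two times may run from different zeros.** A reader might infer that the test is impossible on any reading. Step 4 shows otherwise. This stands as a condition on the conclusion. It does not remove the defect, because the plan names neither zero.
- **The questionnaire after the scan collects pain.** It is scheduled, so the correct count is none of three *timed* scores. It does not supply a 30-minute score.
- **Little depends on this test.** The t-tests and mixed model use the scheduled scores, percentage differences are planned at every time point, and nothing marks the 30-minute test as primary. A reader might infer that the main pain comparisons are undermined; they are not. Nor do the documents show that knowledge of the arm will bias the choice of record. The analysts are stated to work separately from data collection, although that limits their influence on what is recorded rather than on which record is analysed.

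The missing template may contain a 30-minute pain row. If so, the text of Data Collection Procedures disagrees with it and still needs correcting.

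**Conclusion.** The point holds for complete resolution of pain and any other pain-based categorical outcome. As written, the analysis time has no matching timed pain score: 0 of 3, with a gap of 15 minutes to the last one if both times share a zero. That condition is an assumption, because the plan defines no zero; other pairings could bring the two times together but are not stated. The statement about which scores precede contrast also assumes that contrast is given at CT start.

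This is an inconsistency between two sections, not a failure of the trial's main comparisons. No effect on error rate or bias is claimed. It should be corrected because it is cheap to do so and because the choice would otherwise be made later by people who know the arm.

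**What to change.** Make these changes before outcomes are analysed by arm.

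1. In Data Collection Procedures, define time zero for the pain scores as the contrast injection, and keep the baseline score before the study drug.
2. In Data Analysis, for pain-based categorical outcomes, do one of the following:
   - replace 30 minutes with a named scheduled score. The one immediately after contrast best fits the aim of measuring immediate discomfort, with 15 minutes as the later point; or
   - keep 30 minutes and add one 30-minute pain score, counted from the same zero.
3. Keep the vital-sign and adverse-effect records timed from the study drug. They now share one schedule with the pain scores, so moving everything to the contrast zero could lose the timed safety check right after lidocaine.
4. State that no other pain record will be substituted, and bring the data collection template into line.

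The first option in item 2 costs a wording change. The second costs one extra pain score per child, within the existing monitoring window of up to 120 minutes. Treatment and sample size do not change.

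### No pain score is explicitly scheduled for the 30-minute analysis, and the plan does not name the comparison that tests the hypothesis of less pain after contrast

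*Combined protocol and SAP*

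**What the plan says.** Data Collection Procedures contains two assessment schedules. The timed one records pain scores, vital signs and adverse effects "prior to intervention, immediately following intervention, and 15 min following the intervention". The other has no clock times: "A questionnaire will be completed prior to administration of the medication as well as following the CT scan". The section also refers to chart items collected "as shown in the data collection template"; that template is not in the available text.

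*Intervention* is not defined. The Design paragraph calls the study drug the assigned treatment and places it 10 minutes before the CT scan. It then lists pain, pruritus and burning scores as post-intervention. Background and Significance describes participants as children "who can comply with a pre and post IV contrast pain assessment", and the Hypothesis is that lidocaine lowers pain and discomfort after the contrast infusion.

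Data Analysis names no primary outcome, time point or model contrast. It plans:
- an "independent-sample t-test to assess differences in pain scores between the 2 groups at the various intervals";
- a longitudinal model: "Mixed-model linear regression will be used to compare changes in pain numeric rating scale across time points";
- for categorical outcomes, a chi-squared or Fisher test that "will be used to compare outcomes at 30 minutes";
- percentage differences and confidence intervals that "between the treatment groups will be calculated for all time points", with P < 0.05 as the significance threshold.

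**The concern.** The analysis paragraph and the collection schedule do not match. Resolution of pain at 30 minutes needs a pain score at 30 minutes, and neither schedule lists one. The 30 minutes also has no stated origin: it could run from the drug, the contrast or the end of the scan. Whoever runs the analysis would have to choose a substitute score, possibly after seeing the data.

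The hypothesis is about pain after contrast, but the plan tests several times on an equal footing and leaves open which one decides. A favourable result at any of them could be presented as the answer, and the nominal 5% error rate would not apply to that choice.

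A further concern depends on how *intervention* is read. If it means the study drug, the score taken immediately afterwards could come before contrast. A group difference at that moment could not be contrast pain. It could reflect pain already present, since Background and Significance says these scans are usually for suspected appendicitis.

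**Working it through.** The plan gives no sample size, standard deviation, effect size or error-rate calculation, so there is no figure of its own to reproduce and no power loss can be computed. Two checks are possible.

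**Check 1: does any scheduled score fall at 30 minutes?**

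Inputs: drug 10 minutes before CT (Design); timed scores at 0 and 15 minutes after *intervention* (Data Collection Procedures); categorical analysis at 30 minutes (Data Analysis). Infusion length and scan length are not given.

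- Same origin for schedule and analysis: the post-baseline scores are at 0 and 15 minutes and the analysis is at 30. There is no match, whether the origin is the drug, the contrast or the scan.
- Mixed origin: count the 30 minutes from the drug and the scores from the end of CT. With an assumed D minutes from CT start to CT end, the scores fall at 10 + D and 10 + D + 15 minutes after the drug.

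| Assumed D (min) | Scores, min after drug | One at 30? |
|---|---|---|
| 0 | 10, 25 | no |
| 5 | 15, 30 | yes |
| 10 | 20, 35 | no |
| 15 | 25, 40 | no |
| 20 | 30, 45 | yes |

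A match therefore needs two different origins and a particular scan length, and the documents state neither. The post-CT questionnaire has no stated minute, so it could fall near 30 minutes, but nothing plans for that. Monitoring for up to 120 minutes covers vital signs and adverse effects, not pain scores.

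If *intervention* means the study drug, let the infusion last L minutes, with L assumed between 0 and 10. Relative to planned CT start:
- score immediately after the infusion: −10 + L, so −10 to 0;
- 15-minute score: −10 + 15 = +5 counted from drug start, or 5 + L = +5 to +15 counted from infusion end.

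On that reading the first score precedes the planned CT start unless the infusion takes about 10 minutes. If *intervention* means the contrast or the CT, the first score is post-contrast and this issue disappears.

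**Check 2: error rate when several times are tested and none is designated.**

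Assumptions: no true effect at any time; k equally correlated normal test statistics, each two-sided at 0.05 (the plan does not state sidedness); correlation ρ assumed, because the documents give none. With c = 1.96,

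P(at least one significant) = 1 − ∫ φ(z) [Φ((c − √ρ z)/√(1−ρ)) − Φ((−c − √ρ z)/√(1−ρ))]^k dz.

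For ρ = 0 this is 1 − 0.95^k: 1 − 0.9025 = 9.75% for k = 2, and 1 − 0.8574 = 14.26% for k = 3.

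| ρ (assumed) | k = 2 | k = 3 |
|---|---|---|
| 0 (independent) | 9.75% | 14.26% |
| 0.3 | 9.5% | 13.6% |
| 0.5 | 9.1% | 12.5% |
| 0.7 | 8.3% | 10.9% |
| 0.9 | 7.0% | 8.4% |

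The k = 2 column is for the two post-baseline times in the timed schedule. The k = 3 column applies only if the post-CT questionnaire is a separate occasion; if *intervention* is the CT, it may coincide with the score taken immediately afterwards.

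**The case against.** The strongest reply is that the trial will collect what it needs. A post-CT questionnaire is planned, and Background and Significance and the eligibility criteria both refer to pain assessed before and after contrast. Pruritus and burning, listed as post-intervention scores, resemble the contrast effects described in the background. The text therefore leans towards a post-contrast meaning of *intervention*. The unseen data collection template may also carry clock times. This stands, and it rules out three stronger readings.

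- A reader might infer that no data can exist for the 30-minute analysis. The untimed questionnaire or a mixed-origin count could supply a score near 30 minutes. The documents support only the statement that none is explicitly scheduled then.
- A reader might infer that the first post-intervention score is taken before contrast. That holds only if *intervention* means the study drug and the infusion is short, and neither is stated.
- A reader might infer that the analysis mixes pre- and post-contrast results. The t-tests and confidence intervals are planned time by time, so those results stay separate. Only the mixed model could combine times, and its form is not given.

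It can also be said that the error rates rest on assumed correlations, and that scores minutes apart in the same child may correlate strongly. That is fair; at 0.9 the excess over 5% is modest.

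The reply does not remove the core of the point. A template could settle when scores are taken, but the analysis text would still not say which comparison decides. A mixed model across times does not settle it either, because no contrast is named and separate t-tests are planned alongside.

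**Conclusion.** The point holds as a specification gap that should be fixed before the data are analysed. Two faults do not depend on how *intervention* is read: the categorical analysis refers to a time at which no pain score is explicitly scheduled, and no comparison is designated as the test of the hypothesis. The possible pre-contrast score is a third fault only under the study-drug reading, which the text leans against.

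That the false-positive chance exceeds 5% is a safe conclusion for tests that are not perfectly correlated. The particular values, about 7% to 9.5% for two times and about 8% to 14% for three, are illustrations over assumed correlations of 0.9 to 0.3. They count times only. The plan also lists FACES, a 1 to 10 numeric score, a 5-point discomfort scale, pruritus and burning, so fixing the time without fixing the scale would leave several candidate tests. Nothing here shows that the trial lacks post-contrast data.

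**What to change.** Leave drug timing unchanged and make four changes.

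1. Define *intervention*, and reconcile the Design, Data Collection Procedures and Data Analysis text into one assessment table with a stated time origin.
2. Prespecify one already planned post-contrast pain score, on one named scale, as the primary between-group comparison and as the treatment contrast in the mixed model. A natural choice is the numeric rating scale, which Data Analysis already models, taken after the CT scan. If the 15-minute score is shown to be post-contrast it is also a candidate; what matters is that one is chosen in advance.
3. Label other times and scales secondary, and any score taken after the drug but before contrast descriptive.
4. Move the 30-minute categorical analysis to the chosen time point.

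Recording the clock times of drug, contrast and each score would let the schedule be verified, if the template does not already do so.

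The cost is wording in two paragraphs and perhaps a few time fields; no new measurement is needed. The downsides are that results at other times become secondary and that a post-CT score is not at a fixed interval from the drug.
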